Adverse events and unexpected problems involving risks to subjects will be recorded on the online form "Serious and Unexpected Adverse Event and Safety Report" developed by the University of Florida's IRB. This form collects a description of the event, the course of action taken, and specification regarding whether the event was: 1) serious (e.g., requiring hospitalization, resulting in significant disability/incapacity or death); 2) unexpected, and 3) more than likely related to the study interventions/procedures. All serious and unexpected adverse events are to be reported to the University of Florida IRB within 5 working days and to the study's sponsor. Less-serious adverse events will be monitored and reported to the University of Florida's IRB in the study's annual progress review.

Inclusion of Women, Minorities and Children

Inclusion of Women. BC predominantly affects women; thus, only female participants will be recruited (N = 26).

Inclusion of Minorities. All participants will self-report as AA or Black women.

Inclusion of Children. Children will not be included in the proposed study as the focus of this application is to investigate mechanisms of gratitude, well-being, and exercise readiness associated with older adult survivors of BC.

8. **Conflict of Interest**: The principal investigator declares that there is no conflict of interest in conducting this study.

References

- 2. American Cancer Society. Cancer Treatment & Survivorship Facts & Figures 2019-2021. American Cancer Society. https://www.cancer.org/content/dam/cancer-org/research/cancer-facts-and-statistics/cancer-treatment-and-survivorship-facts-and-figures-2019-2021.pdf. Published 2019. Accessed.
- 4. Lee J. A Meta-analysis of the Association Between Physical Activity and Breast Cancer Mortality. *Cancer Nurs.* 2019;42(4):271-285.

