Aim 1. Assess the feasibility and acceptability of a gratitude journaling intervention using a pilot randomized controlled trial (RCT) two-group parallel design over eight weeks. We hypothesize that among the 28 participants 1) at least 80% of the participants in both arms will report the study to be acceptable, 2) biomarker collection will be completed in at least 80% of the surveys and the retention rate will be 80% in each group, and 3) physical activity, health markers, gratitude, well-being, and distress will improve over time in the gratitude intervention group than those in the attention control group.

Aim 2. Describe differences and distributions of outcome variables and effect size for the gratitude journaling intervention compared to the attention control group on dispositional gratitude, spiritual well-being, psychological distress, exercise readiness, mental and health behaviors in AA women (Superwoman Schema), and inflammatory biomarkers from baseline to post-intervention.

Research Plan:

We will conduct a pilot feasibility study for the gratitude intervention using a two-group parallel randomassignment experimental design to achieve our aims. We will use resources from the Clinical Research, Metabolism and Translational Science, and Biostatistics Cores of the UF Older Americans Independence Center's (OAIC) / UF Clinical and Translational Science Institute (CTSI) to conduct this study.

Study Participants: As per the recommendation of Julious⁴⁸ for 14 participants per group for a pilot study due to no prior information to base a sample size, we will recruit 28 participants for this two-group study to account for a potential attrition rate of 10%. We will recruit AA women from all socioeconomic groups with a history of BC Protocol

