treated with chemotherapy using organic social media recruitment, flyers ,multiple specialized recruitment strategies from the OAIC Clinical Research Core - Claude D. Pepper Center Participant Registry (IRB201601352), UF Health Cancer Center Community-Partnered Cancer Disparities Research Collaborative (CDRC), UF Health Cancer Center Community Outreach and Engagement, UF Healthstreet, Integrated Data Repsitory and UF Consent2Share Registries. Potential participants will be screened for eligibility via telephone. Eligible participants will be English-speaking, self-reported AA/Black, postmenopausal women with a history of BC (Stage I–IV) who are 3 months to 6 years post-adjuvant chemotherapy. Women on hormonal therapies and anti-human epithelial receptor 2 (HER-2) therapy will be included. Exclusion criteria include self-reported regular meditation or gratitude practices (more than once a week for at least a month) or currently meeting the Centers for Disease Control and Prevention (CDC)'s physical activity guidelines. Women will be compensated \$100 within two time points for their participation.

Study Design: We will adhere to intervention fidelity using the five standard NIH recommendations for intervention fidelity: 1) design of the study; 2) intervener training; 3) treatment delivery; 4) treatment receipt; and 5) treatment enactment.

NIH Recommendations	Description of Treatment Fidelity (Both Arms)
Design of study	To reduce variability in outcome measurement, we will train our research assistant
	and research intern using a detailed intervention manual to instruct the participants
	on how to provide journaling education.
	The interventional manual will include detail on how to use the journal prompts specific to the treatment group (gratitude) and control group (general memories). The prompts are included in a custom-designed journal (i.e., a gratitude-specific journal and a general memory journal) with dates and prompt listed inside each journal. The journal will include 1-2 major physical activity goal page, and an exercise educational resource to promote exercise readiness and self-efficacy.
	Additional forms to be used for data collection will be appropriately designed to encourage the collection of good quality data. They will be user-friendly, self-explanatory, and clearly formatted.

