Data Collection and Study Procedures: After screening for eligibility and collection of verbal consent, we will schedule an in-person appointment to collect baseline data, including collection of a blood sample (see Table 1 for measures and variables to be collected). Before the appointment, we will send demographic and cancer history questionnaires and self-report instruments (listed below) to participants for review. Informed written consent will be obtained at the in-person appointment, and an electronic survey will be sent following completion of the first appointment. After baseline (T1) data collection, participants will be randomized to either the gratitude journaling intervention or attention control group in a 1:1 ratio using online randomization software (http://randomization.com), and block randomization to ensure equal distribution between groups. The PI will inform participants of their group assignment and provide intervention details. The research assistant and biostatistician will be blind to group allocation. Participants will begin their daily intervention within 1 week of completing T1 data collection. They will also be scheduled for their T2 data collection appointment, which will occur 8 weeks after the start of the intervention and will include the same measures as baseline excluding the demographic and cancer history questionnaires. Data will be stored in Qualtrics on a secure university server and password protected with the assistance of the Biostatistics Core.

Blood Collection, Processing, and Storage: Blood samples will be obtained by a registered nurse or phlebotomist using the CTSI's standard protocol at the UF Clinical Research Center. After a ten-minute rest period, up to 10 ml of blood will be drawn. No more than two attempts will made to obtain blood samples with any participant. Blood samples will be collected, processed and stored with the OAIC Metabolism and Translational Science Core in the UF Clinical Research Center.

Table 1. Study Measures.

Outcome (Time Points)	Measure/Description
Demographics (T1)	Age, sex, education, marital status, body mass index; cancer- and treatment-related variables
	including time since diagnosis, cancer stage, grade and other disease-related variables including
	hormonal and HER2 status, surgical type, chemotherapy, radiotherapy, and cancer treatment.
Dispositional gratitude	The Gratitude Questionnaire-6 (GQ-6), a well-validated, self-administered 6-item scale, is

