(T1, T2)	designed to measure four facets of dispositional gratitude: ⁴⁹ (a) intensity, (b) frequency, (c) span
	and (d) density. Each item is rated on a 7-point Likert-type scale ranging from 1 (strongly
	disagree) to 7 (strongly agree).
Spiritual Well-Being	The Functional Assessment of Chronic Illness Therapy - Spiritual Well-Being 12 Item Scale
(T1, T2)	(FACITsp12) is a 12-item scale designed to assess spiritual well-being over the past 7 days in a
	population with a chronic illness. ⁵⁰ Items are rated on a Likert-type scale ranging from 0 (not at all)
	to 4 (very much).
Distress	The Perceived Stress Scale (PSS), used to measure stress, consists of 10 items rated on a 5-
(T1, T2)	point Likert scale ranging from 0 (never) to 4 (very often) during the last month.

Outcome (Time Points)	Measure/Description
Superwoman schema	The Giscombe Superwoman Schema Questionnaire (G-SWS-Q) was developed to measure
(racial and gender	components prominent in the superwoman schema construct. ^{6,51} It contains 35 statements rated
identity)	from 0 (not true) to 4 (true all the time) across the 5 subscales of (1) obligation to present an image
(T1, T2)	of strength, (2) obligation to suppress emotions, (3) resistance to being vulnerable, (4) intense
	motivation to succeed and (5) obligation to help others. Higher scores indicate higher agreement
	with the identity.
Exercise readiness (self-	Exercise readiness will be assessed using the Stage of Motivational Readiness for Physical
efficacy and stages of	Activity questionnaire, a highly reliable instrument with 5 items that classify a person as being in
exercise behavior	the pre-contemplation, contemplation, preparation, action, or maintenance stage of exercise
change) (T1, T2)	behavior change. ⁵²
TNF-α, IL-6, GDF15 (T1,	Luminex panel
T2)	
CRP (T1, T2)	Enzyme-linked immunosorbent assay (ELISA) kit
Treatment satisfaction	The Client Satisfaction Questionnaire (CSQ) is a standard measure used across health care
(T2)	delivery and will be used to assess the acceptability of the gratitude intervention. ⁵³

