Separate two-by-two mixed-effects general linear models (GLMM),⁵⁴ comprised of effects for treatment, time, and treatment-by-time interaction, will be used to estimate effect sizes for each of the outcome variables. The distribution of residuals will be evaluated for the tenability of model assumptions, and, where necessary, remedial measures such as Box-Cox transformations will be applied. CONSORT guidelines for intent-to-treat principles will be used for hypothesis testing to manage missing data related to attrition. We will determine differences between groups using t-tests.

6. Possible Discomforts and Risks: Protection of Human Subjects

PI Version: 09/21/2022

According to federal regulations and NIH policy, applications that propose to involve human subjects must address risks to human subjects (human subject characteristics, involvement and design; sources of materials; and potential risk); adequacy of protection against risks (recruitment and informed consent and

Protocol IRB version 03.09.04 protections against risk); potential benefits of the proposed research (are potential risks to subjects reasonable in light of anticipated benefits?); the importance of the knowledge to be gained; and a data- and safety-monitoring plan/board. We address each of these requirements below.

Risks to Human Participants

Inclusion/Exclusion Criteria. Table 2 lists study inclusion/exclusion criteria. Exclusion criteria are designed to prevent inclusion of participants who would experience discomfort or harm during collection of blood or other data and to protect the data integrity of the participants.

Table 2. Inclusion and Exclusion Criteria.

Inclusion Criteria

- Self-report as AA or Black
- English speaking
- History of BC (Stage I–IV); 3 months to 6 years post-adjuvant chemotherapy
- Participants on hormonal therapies or HER-2 therapy are acceptable

Exclusion Criteria

- Self-reported regular meditation or gratitude practices (more than once a week for at least a month)
- Meeting the CDC's physical activity guidelines (at least 150 min of moderate-intensity aerobic physical activity or 75 min of vigorous-intensity physical activity, or an equivalent combination each week)

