Blood-draw collection. Although generally safe, blood-draw collection procedures can confer limited risks, including that a participant will experience pain or discomfort. To minimize discomfort, we will make no more than two attempts per time point to obtain blood samples with any one participant.

Onsite adverse events. In the event of any of the following adverse events, we will immediately notify a physician and the IRB: 1) deaths, 2) falls, or 3) health events that result in immediate hospitalization or medical care.

Attrition. Given the success of the studies conducted at the UF OAIC Clinical Research Core, we do not expect any recruitment issues. However, since this proposal requires two visits to the institute, we are anticipating 5%–10% attrition. We will thus gather all primary data (blood draw and electronic questionnaires) during the T1 visit. At the T2 visit, we will collect another blood draw and the electronic questionnaires and conduct exit interviews and administer the CSQ to evaluate usability, usefulness, and participant satisfaction. Both structured and openended questions will be used to assess participants' perception of the intervention's content, value, structure, and burden. To further minimize attrition, we will (1) educate participants during the initial telephone screening about the importance of committing to the study, (2) obtain complete contact information (including alternative email addresses and phone numbers), (3) place a reminder call and/or email (if available) 2 days before the scheduled visit, and (4) provide compensation upon completion of each visit.

Inadequate Sample Size. Since this is a pilot feasibility study, which requires a relatively small sample, it may be underpowered to detect statistically significant differences in outcome measures. However, it will provide the information necessary to design future adequately powered efficacy studies.

Adequacy of Protections Against Risks

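### Aim 1 hypothesis 3 predicts better physical activity than control, but no scheduled measure is designated as that outcome and none records how much activity is done

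*Combined protocol and SAP*

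**What the plan says.** Section 5, Aim 1, hypothesis 3 states that "physical activity, health markers, gratitude, well-being, and distress will improve over time in the gratitude intervention group", in comparison with the attention control group. The opening of Section 5 also makes promotion of physical activity part of the overall objective.

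Table 1 lists what is collected. The row nearest to the hypothesis reads "Exercise readiness will be assessed using the Stage of Motivational Readiness for Physical" Activity questionnaire, and it classifies a woman as being in "the pre-contemplation, contemplation, preparation, action, or maintenance stage of exercise" behaviour change. Under Data Collection and Study Procedures, the T2 visit "will include the same measures as baseline excluding the demographic and cancer history questionnaires".

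Under Data Analysis, mixed models with treatment, time and their interaction "will be used to estimate effect sizes for each of the outcome variables". The physical-activity variable is not identified there.

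An amount of activity appears for participants only in Table 2, as an exclusion for women who already meet the national guideline: "at least 150 min of moderate-intensity aerobic physical activity or 75 min of vigorous-intensity physical activity". On timing, Study Participants says: "Potential participants will be screened for eligibility via telephone".

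**The concern.** A hypothesis that names an outcome needs a variable behind it. Here the outcome listed first in hypothesis 3 has none. If the plan is followed exactly, week 8 arrives with nothing that the protocol calls physical activity, and that part of the hypothesis is either left unanswered or answered with something the protocol calls by another name.

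Readiness and activity are different constructs. A woman can move from contemplation to preparation without walking further, and can add an hour a week without changing stage. The action and maintenance stages say something about behaviour, but only coarsely.

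There is also a planning cost. The section on inadequate sample size says of the pilot that "it will provide the information necessary to design future adequately powered efficacy studies". As scheduled, it gives no standard deviation and no completion rate for amount of activity, should a later trial want that endpoint.

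**Working it through.** No figure in the plan is in dispute, so the check is a comparison of texts.

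**Step 1: rows of Table 1.** Demographics and cancer history (T1 only); GQ-6; FACIT-Sp-12; Perceived Stress Scale; Superwoman Schema questionnaire; exercise readiness; TNF-α/IL-6/GDF15 panel; CRP; Client Satisfaction Questionnaire (T2 only). That is 1 + 7 + 1 = 9 rows, seven of them at both visits. Rows designated as physical activity: 0 of 9. Rows recording minutes, steps or frequency: 0 of 9. Rows bearing on activity indirectly: 1 of 9 (readiness, five stages).

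**Step 2: hypothesis 3 against Aim 2 and Table 1.**

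| Hypothesis 3 term | Nearest Aim 2 item | Table 1 measure |
|---|---|---|
| gratitude | dispositional gratitude | GQ-6 |
| well-being | spiritual well-being | FACIT-Sp-12 |
| distress | psychological distress | Perceived Stress Scale |
| health markers | inflammatory biomarkers | cytokine panel, CRP |
| physical activity | none by that name; exercise readiness is closest | stage questionnaire, labelled readiness |

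Four terms reach a measure of the same construct. The fifth reaches only a related one, and no sentence says that it stands in for activity.

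**Step 3: other places an activity variable could come from.**
- T2 repeats the baseline set, less demographics and cancer history, and adds satisfaction and an exit interview. The interview covers perceptions of content, value, structure and burden.
- The fidelity table scores journals on how often and how much was written.
- Telephone screening must ask about activity in some form to apply the Table 2 exclusion. Nothing says the answer is kept as a baseline value, and it is not asked again.

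**Step 4: the model.** It is fitted to each outcome variable. With no variable designated as physical activity, none enters under that name.

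**Step 5: burden of the repair.** With 28 women and 10% attrition (Study Participants), 28 × 0.90 = 25.2, so about 28 + 25 = 53 completions over the two visits. With the 26 given under Inclusion of Women, 26 × 0.90 = 23.4, so about 26 + 23 = 49. The finding does not depend on which total is right.

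**Separate check: what controls receive.**
- The fidelity table is headed as covering both arms. It describes both journals and then says, without naming an arm, that the journal holds an activity goal page and an exercise resource.
- The same table calls the baseline training content uniform.
- Under Gratitude Intervention, the brochure and goal setting are introduced without naming an arm. The goal-setting modules then appear in the paragraph on the gratitude arm.
- The control paragraph gives a memory prompt and neither includes nor excludes the rest.

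Both readings are open: the arms may differ by the prompt alone, or by the prompt plus goal setting and education.

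**The case against.** The strongest reply is that the intended variable is evident. Hypothesis 3 uses loose labels throughout, its other four terms pair off with Aim 2, and exercise readiness is the natural partner for the fifth. The instrument has physical activity in its name, and the hypothesis never promises minutes. On this view the fault is wording only.

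Part of this stands. Table 1 offers only one candidate, and it can be named in advance. A reader might infer that the team would be free to pick a proxy after seeing the data; the documents do not support that, since there is nothing to pick among. The reply also shows that rewording is a sufficient repair. But the pairing is inferred and stated nowhere, Aim 2 lists readiness and omits activity, and the overall objective speaks of activity itself. If readiness was meant, the hypothesis is worded wrongly; if activity was meant, the measure is missing. Either way the text needs a change.

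It can also be said that this is a pilot, acknowledged as possibly underpowered, and that no passage fixes activity amount as the endpoint of the later trial. That is correct. The missing standard deviation is a lost opportunity, and a breach of the pilot's stated purpose only if activity amount is assumed to be the next endpoint.

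**Conclusion.** The point holds for one term of one hypothesis. Physical activity is predicted to improve over control, yet none of the nine Table 1 rows is designated as that outcome or records its amount at either of two visits. The only related measure is a five-stage readiness scale. Confidence is high, because this rests on the text alone. It is worth correcting before data collection.

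A reader might infer that the pilot therefore cannot meet its aims. The documents do not support that. Aim 2 names exercise readiness, which is measured at both visits, and the feasibility criteria concern eligibility and completion of assessments. Nor is it right that nothing behavioural is captured, since the upper readiness stages carry some such information.

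The arm-content question is a separate ambiguity, held with moderate confidence. It bears on what an exercise-readiness difference would mean: the effect of gratitude prompts alone, or of prompts with goal setting and education. It is not a contradiction, and this review does not say which content is right.

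**What to change.** **Preferred.** Add to Table 1, at T1 and T2, a brief self-report of weekly moderate and vigorous minutes, in the units of the Table 2 exclusion, and name it as the physical-activity outcome in hypothesis 3. Use it for estimation only: the between-arm estimate with its 95% confidence interval, the standard deviation and item completion. Women meeting the guideline are excluded, so zeros are plausible; report the median, interquartile range and number at zero as well.

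Cost: a few minutes per visit (an assumption), about 53 completions, and no extra visits or participants. The drawback is self-report error, which could differ by arm if only one arm is given activity goals.

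**Alternative, if no measure is added.** Before data collection, reword the term in hypothesis 3 as exercise-readiness stage, and state that it will be analysed as a five-level ordinal outcome instead of by the general linear model and t-tests. This changes wording only, and gives up any information on amount.

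**Separately.** Reconcile the fidelity table, the Gratitude Intervention text and the control-arm paragraph into one statement of what each arm receives, and word the Aim 2 contrast to match. This too is a wording change.

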Dispositional gratitude, defined as an appreciation of the positive aspects of life, is associated with better physical health among older adults. 11 Research has shown that practicing gratitude can positively impact levels of inflammatory biomarkers and individuals who practice gratitude are more likely to engage in more moderatevigorous exercise. 12-18 The design of the proposed 8-week gratitude journaling intervention is based on the broaden-and-build theory of positive emotions, 19 which posits that dispositional gratitude serves to broaden people's thought-action repertoire, leading them to build physical and physiological resources that improve longterm well-being. 20 The intervention will also include a goal-setting component to promote exercise readiness and examine the Superwoman schema. Similarly adapted psychological interventions have led to improved physical activity in patients with cardiovascular disease. 21,22 Among majority-European American BC survivors, gratitude is associated with reduced psychological distress and enhanced spiritual well-being. 23-26 A significant gap remains, however, in the knowledge of the mechanisms underlying gratitude's link with physical health especially its association with physical activity and inflammatory biomarkers in older AA BC survivors, who are at the highest risk of mortality and morbidity. Examining the preliminary feasibility and efficacy of a culturally tailored intervention to improve well-being and exercise readiness among female AA BC survivors is a critical first step toward the design and funding of a larger randomized controlled trial to test the effects of the intervention on biobehavioral outcomes.

4. Background:

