	The PI and study staff will provide any technical assistance regarding journaling for the participants and a direct number and email address for any additional issues that may potentially arise.
Intervener Training	Because all training content explained at baseline is uniform, and the journaling will be recorded in the journals at least twice a week, there will be no deviance in the provision of the program across participants.
Treatment Delivery & Receipt	A study-specific protocol will be developed and explicitly followed. Dosing (times per week the participant completed journals and practice) will be meticulously tracked by evaluating: the number of journal entries at least twice a week and the number of words written per journal entry in the hardcover journal. The journal will be given at week 0, and the journal will be collected after week 8 during the final appointment.
	We will limit the entries to six memories, with a target goal of 10-15 minutes spent journaling, and no set schedule (having entries occur in the morning or evening). The study staff will provide a weekly email reminder to enter a journal entry at least twice a week.
Treatment Enactment	We will follow participants from week 0 to week 8 to determine sustained use of the intervention (intermediate output).

Gratitude Intervention: The proposed study builds on Emmons and McCullough's original gratitude journaling intervention.⁴⁹ The original intervention, mostly undergraduate psychology students, did not include a goal-setting exercise and conducted daily gratitude journaling. However, prior cardiovascular health studies have found that interventions pairing optimism and gratitude with education and systematic goal-setting related to physical activity led to more physical activity, fewer hospital readmissions, and improved levels of inflammatory

Protocol Page 4 of 12

biomarkers.³⁶ Therefore, this study will pair the use of goal setting and physical activity education and to reduce the burden of journaling for cancer survivors and the participants will journal at least twice a week. During the initial session, the Principal Investigator or research assistant will provide a journal kit and an educational physical activity brochure to assist in setting 1-2 physical activity goals during the study period.

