For the gratitude intervention, each participant will receive a gratitude journal for the eight-week period and will have the following journaling prompt to complete for at least twice a week for a duration of 10-15 minutes: "There are many things in our lives, both large and small, that we might be grateful about. Think back over the day and write down on the line below all that you are grateful for today" (maximum six reasons). The educational component on goal setting will drawn from the American Cancer Society's *Nutrition*, *Physical Activity*, and *Cancer* toolkit. Participants will be able to choose the order in which they complete the goal-setting modules. Both of these exercises will be administered at least twice a week over 8 weeks, preferably at the same time each day with a target goal of 10-15 minutes. Each participant will have the option to complete either a paperback journal or an electronic journal via Qualtrics.

For the attention control arm, participants will receive a receive the following general journaling prompt for at least twice a week for no more than 15 minutes: "What are some memorable events that happened to you today, big or small (maximum six memories). Write a brief statement about it. At the end of the intervention, at week 8, we will collect the journal for treatment fidelity. We will give the option to mail the journal back to the participant as a keepsake if requested.

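### Does it matter that the protocol does not say whether the control journal also carries the physical-activity goal page and exercise resource?

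*Combined protocol and SAP*

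**What the plan says.** The fidelity table in the Research Plan (Study Design) has a column headed "Description of Treatment Fidelity (Both Arms". Its first row describes two products, "a gratitude-specific journal and a general memory journal", and then states: "The journal will include 1-2 major physical activity goal page, and an exercise educational resource to promote exercise readiness and self-efficacy". No arm is named in that sentence.

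The other relevant places are:

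- Abstract: "The intervention will also include a goal-setting component to promote exercise readiness". The Significance text and the Figure 1 caption in Background likewise describe one intervention that combines gratitude with goal setting.
- Gratitude Intervention, opening paragraph: "this study will pair the use of goal setting and physical activity education". At the initial session participants get a journal kit and "an educational physical activity brochure to assist in setting 1-2 physical activity goals during the study period". The heading is that of the experimental arm, but the sentences name no arm.
- Gratitude Intervention, paragraph on the gratitude prompt: "Participants will be able to choose the order in which they complete the goal-setting modules". The prompt and the modules are then scheduled together as a pair of exercises.
- Control paragraph: "For the attention control arm, participants will receive a receive the following general journaling prompt". The memory prompt follows; goal setting is neither given nor ruled out.

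Aim 2 asks for effect sizes of the gratitude journaling intervention against attention control, with exercise readiness among the outcomes. Table 1 schedules that measure at T1 and T2.

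**The concern.** The goal page and exercise resource are there to raise exercise readiness, which is an Aim 2 outcome and appears in the study title. If the control journal contains them too, the between-arm difference reflects mainly the gratitude prompt. If it does not, the difference reflects gratitude and goal setting together. Two arms cannot separate those components afterwards.

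The pilot is meant to inform later efficacy trials (Inadequate Sample Size), and the Innovation paragraph foresees gratitude journaling as one part of a multimodal programme. A designer who took a package effect for a gratitude effect, or the reverse, would plan on the wrong quantity.

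**Working it through.** **1. What the effect size would mean under each reading.** The Data Analysis section fits treatment, time and their interaction. The interaction is the mean T1-to-T2 change in the gratitude arm minus that in the control arm. As a simple additive sketch, let *g* be the effect of the gratitude prompt relative to the memory prompt, *s* that of the goal page and exercise resource, and *m* that of the modules. The brochure goes with *s* or *m*, depending on who receives it.

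| Reading | Gratitude arm gets | Control arm gets | Interaction estimates |
|---|---|---|---|
| A: all material in both arms | prompt, *s*, *m* | memory prompt, *s*, *m* | *g* |
| B: all material in the gratitude arm only | prompt, *s*, *m* | memory prompt | *g* + *s* + *m* |
| C: page and resource shared, modules not | prompt, *s*, *m* | memory prompt, *s* | *g* + *m* |

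Each is a randomised contrast between assigned programmes, so each can be estimated without bias from the allocation. The protocol gives no value for *g*, *s* or *m* on exercise readiness, so the gap between the readings has no computable size. The materials may also overlap: the resource, the brochure and the toolkit-based modules are not shown to be separate items. Counting how many differ between arms would therefore mean little.

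**2. Which reading the text favours.** The Abstract, Significance, the Figure 1 caption and the Gratitude Intervention section all describe a combined intervention. The Data Analysis section also names gratitude and goal-setting exercises together when it explains the satisfaction questionnaire. The control paragraph mentions neither goals nor education. On the other side is one table sentence with a singular noun and no arm. The table's remark that baseline training content is uniform adds little: it concerns what is explained at baseline, and the same table says the prompts differ by group. The text therefore leans to B, with C possible if the table sentence is taken to cover both journals. A is the hardest to fit with the gratitude and control paragraphs.

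**3. What depends on the answer.**

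- Sample size: with 12 per group (from the title of the cited pilot reference) and 10% attrition, 12 / (1 − 0.10) = 13.3, rounded up to 14 per group, and 2 × 14 = 28. This reproduces the stated total, and no input concerns arm content.
- Allocation (1:1), model terms and the feasibility thresholds (75% and 80%) do not refer to the control journal's content.
- Precision: for a standardised difference between two means, taking the SD as 1, the approximate 95% half-width is 1.96 × √(2/n). With n = 14 per arm this is 1.96 × √(2/14) = 0.74; with n = 12 it is 1.96 × √(2/12) = 0.80. Attrition of 10% leaves 14 × 0.90 = 12.6 per arm, between the two. The estimate is descriptive and wide whichever contrast it measures.

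**4. Whether the answer can be recovered.** The journals are custom-made for each arm, and the protocol has them collected at week 8. The intervention manual, which is not among the documents, is to cover both arms' journals. Which pages a journal held is a matter of record and needs no inference from the data.

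**The case for a change.** The strongest case for a change is that no reading fits every sentence comfortably. Reading B needs the singular noun in a both-arms table, just after two journals are named, to mean only one of them. Reading A has to explain away the placement of the modules. Nothing states outright what the control arm does or does not receive. Staff handing out kits need one instruction, a reader of the protocol cannot see the manual, and the outcome affected is the one the material is meant to move. Aim 1's third hypothesis, on physical activity, is touched as well.

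What stands is that the table sentence is loosely worded and that the result must be described by what actually differed between the arms. The rest is weaker. The Abstract defines the intervention as including goal setting, so Aim 2's label names a package and does not claim that gratitude acts alone. The passage on gratitude and physical-activity behaviours, under Importance of Knowledge to Be Gained, is a rationale for a later model and not a planned conclusion from the Aim 2 estimate. The texts set an implied inclusion against silence; they do not make opposing statements. A table of goal-page completion by arm would be an extra, and collected paper journals alone would miss entries made in the Qualtrics option.

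**Conclusion.** The gap is real but minor, and the plan can stand. It is missing descriptive detail: the comparison of the assigned programmes is sound under every reading, and no sample size, model, threshold or decision rule changes. An analyst would list each arm's contents from the manual and the journals, and would report the exercise-readiness effect size as the effect of whatever differed between them.

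This rests on two assumptions: that the manual or the journals show what each arm received, and that Aim 2 stays descriptive, as written. The possible shift in the effect size between readings is unknown and cannot be bounded from the documents.
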